## 2. STUDY OBJECTIVES

### 2.1 PRIMARY OBJECTIVES

- To develop and validate a diagnostic score for iGBC in patients undergoing cholecystectomy for benign indications.

### 2.2 SECONDARY OBJECTIVES

- To establish the pre- and peri-operative risk factors for iGBC and BHC in a UK population
- To define the incidence of iGBC and BHC in a UK population
- To explore the views of patients and healthcare professionals regarding the risk of iGBC in routine cholecystectomy and their acceptance of selective histological analysis of the gallbladder

### 2.3 OUTCOME MEASURES

- Rates of iGBC
- Rates of BHC
- Internal pilot: Feasibility of conducting a large multi-centre prospective study.
- Internal pilot: Feasibility of developing a diagnostic scoring system for the diagnosis of incidental gallbladder cancer based on pre- and intra-operative factors.
- Completed study: Validation of a diagnostic score for incidental gallbladder cancer.

## 3. STUDY PARTICIPANTS

**Cross sectional study:** All adult patients undergoing routine cholecystectomy within the study period at participating sites (subject to inclusion and exclusion criteria below).

**Qualitative study:** Participants will be recruited from patient lists at study sites, from within the NHS and through specialty association mailing lists. Each group will consist of participants who have been

Date and Version No: 04/11/2024; Version 1.3

purposively selected to represent a cross section of the population. For example, by incorporating a range of ages or career stages, rural and urban settings, and from primary, secondary, and tertiary care settings. Contingency arrangements, including convenience sampling and snowballing, are outlined in section 6.2.

Participant groupings will include:

1. Patients with a history of benign gallbladder disease, either pre- or post-cholecystectomy including, if possible, at least one post-operative patient with an iGBC diagnosis (5-7 pre-operative and 5-7 post-operative)
2. Surgeons who undertake adult cholecystectomy as part of their routine practice, including, if possible, at least two who have experience with patients with iGBC (8-10 participants)
3. Healthcare staff involved in non-clinical management and decision-making (3-5 participants)
  - a. Clinical Commissioners
  - b. Managers

### **3.1 SCREENING PROCEDURES**

#### **Cross-sectional study:**

All patients aged 18 and over who are being considered for cholecystectomy at participating sites during the study period should be screened.

#### **Qualitative study:**

Participants will be purposively selected to represent a cross-section of the relevant populations, for example, by incorporating a range of ages or career stages, rural and urban settings, and primary, secondary, and tertiary care settings.

### **3.2 INCLUSION CRITERIA**

#### **Cross-sectional Study:**

All adult patients (>=18 years of age) undergoing cholecystectomy (including subtotal and remnant cholecystectomy) for benign indications:

- Symptomatic Gallstone Disease (includes Gallstone Pancreatitis)
- Biliary Dyskinesia

Date and Version No: 04/11/2024; Version 1.3

### **Embedded Qualitative Study**

Consenting adult participants (>=18 years of age) will be purposively selected into groupings, which will include,

- Patients with a history of gallbladder disease, either pre- or post-cholecystectomy, including, if possible, at least one post-operative patient with an iGBC diagnosis (10-15 participants)
- Surgeons who undertake adult cholecystectomy as part of their routine practice, including, if possible, at least two who have experience with patients with iGBC (8-10 participants)
- Healthcare staff involved in non-clinical management and decision-making (5-8 participants)
  - Examples include,
    - Clinical Commissioners
    - Managers
    - Histopathologists

### **3.3 EXCLUSION CRITERIA**

#### **Cross-Sectional Study:**

Participants may not enter the study if ANY of the following apply:

- Imaging suspicious for/confirming type III/IV Mirizzi syndrome.
- History of gallbladder or biliary tree malignancies
- Any pre-operative clinical suspicion of Gallbladder or biliary tree malignancy, (even if subsequently dismissed or disproven)
- Presence of Gallbladder polyps  $\geq 5\text{mm}$
- Biliary tree abnormalities, including Primary Sclerosing Cholangitis and Choledochal Cysts
- Patients undergoing cholecystectomy as a part of, or incidental to, another procedure.

#### **Embedded Qualitative Study:**

Participants may not participate in interviews if ANY of the following apply:

- Unable to consent, or to communicate consent.
- Unable to undertake interview in English, despite reasonable support measures.

Date and Version No: 04/11/2024; Version 1.3

## 4. STUDY DESIGN, PROCEDURES, AND INTERVENTIONS

### 4.1 STUDY DESIGN

Multi-centre, cross-sectional study for diagnostic modelling with an integrated internal pilot, an embedded, parallel, interview-based, qualitative study, and an adaptive design.

The internal pilot and parallel qualitative workstreams will form a feasibility phase of this study (fP-iGBC). Following this feasibility phase, data collection will pause for 18 to 24 months to allow time for analysis of the feasibility phase, additional funding to be secured, expansion of the study team and for centres to be recruited and registered.

### 4.2 RECRUITMENT

#### Cross-Sectional Study

Patients will be identified from waiting lists and emergency admissions within the relevant departments of participating centres during the study period by clinicians undertaking cholecystectomy and those participating in the research (all of whom will be members of the direct care team). As data collection is non-consented, all patients who pass screening against the [inclusion](#) and [exclusion criteria](#) may be recruited, however patients will be able to [opt-out of inclusion in the study as detailed in section 4.3](#), below.

#### Qualitative Study

Patients will be recruited from existing patient waiting and clinic lists and historical patient lists at participating sites. Professional participants will be recruited through speciality association mailing lists, direct approach and those who have expressed an interest in participation in the recruitment stages of the cross-sectional study.

Where potential participants are identified by a collaborator at a participating site, the collaborator will make initial contact with the potential participant to inform them about the study and to invite them to take part in an initial conversation with the central research team. If they are willing to receive more information, the collaborator will ask the potential participant to contact the central research team either by telephone or email, on receipt of which the central research team will take over contact with potential participants to undertake a formal invitation to participate and the informed consent process, as laid out below. Collaborators may alternatively offer to share a contact detail (e.g. an email address or a telephone number) with the central study team, using the encrypted NHS.net email, with the express consent of the potential participant.

#### 4.3 CONSENT

##### **Cross-sectional Study**

Data will be collected from patients and patient records without their consent. Patients will be informed about the study and provided with an opt-out mechanism as outlined below.

##### *Rationale for non-consented data collection.*

The cross-sectional component of this study exclusively requires the collection of de-identified information which would normally be recorded during patient care. This will be extracted from the patient's record by members of the direct care team. The volume of patients required is felt to make individual consent impractical and prohibitively expensive, and would therefore prevent sufficient recruitment. It is subsequently felt to be both justified and necessary to collect the de-identified data without individual patient consent, as per the Confidentiality Advisory Group pre-application checklist, and guidance received in communication with them.

##### *Local arrangements for informing patients about the study.*

When data is collected without informed consent, it is good practice to publicise the study and provide a mechanism for patients to opt-out. Participating units will be required to display notifications (see example in appendices) in appropriate areas, such as outpatient, inpatient, and pre-operative areas. These notifications must include the contact details of the local study team and must expressly state the right to opt-out. Following feedback from our PPIE consultation, we recommend that consenting clinicians inform patients of their eligibility for inclusion, and right to opt-out of the study. This is especially important in the event that a patient does not speak English and is being consented for surgery with the help of a translator (see below). Clinicians in participating units should direct patients to further information, such as the website, a poster, or the PIS if asked. Whilst it will not be mandatory, clinicians may wish to record that the patient has been informed, for example by noting the conversation in the patient's record, on a clinic letter or other clinical documents related to the episode of care.

##### *Patients who do not speak English.*

Patients who do not speak English should be informed of the study during the operative consent conversation, which is normally with a translator. Within the feasibility phase, there is no specific information available in languages other than English. If and where there is any doubt over the participant's understanding, the participant should be recorded on RedCAP as having opted out, given

Date and Version No: 04/11/2024; Version 1.3

that other opportunities for that patient to opt out may be more limited than for those who speak English. Provision will be made to ensure that this reason can be specifically identified, to inform whether multi-lingual participant information sheets should be funded and developed following the feasibility phase. Welsh Language information will be developed following the feasibility phase, if and where centres in Wales participate.

*National arrangements for informing patients about the study.*

During periods of recruitment and data collection, the central study team will post monthly notices of the study to Twitter/X (see example in appendices), and maintain notifications on the website. Collaborating units, are advised to share these notifications, which will include a link to the study website where the PIS, and information about opting-out of the study, will be posted. Following PPIE consultation, notifications will make a distinction between the pilot phase and the full national study.

*Arrangements for patient opt-out.*

Patients have a right to opt-out of the study. As the central research team will not have access to identifiable patient information, it will not be possible for the opt-out mechanism to be centrally administered. Instead, local study teams will be required to field requests for study opt-out. The contact details for the study team at each unit will be made available on local notifications, and on the study website. On receiving a study opt-out request from a patient, units are required to respond and confirm the request within ten working days. In case of a non-response from the local unit, patients will be able to contact the central study team via the study website. This will require the patient to share a single contact address (such as a telephone number or email address) with the central study team, which will in turn be shared with the local unit. The central study team will contact the local team by any or all additional means at their disposal and will require the local team to confirm the opt-out directly with the patient, and then confirm with the central team. As a contingency, and to safeguard patients, in the event that contact cannot be established with the local team, data entry by collaborators in that unit will be paused and data from that unit will not be included in export, until the opt-out request has been satisfactorily fulfilled.

If an eligible patient exercises their right to opt-out before they are identified for inclusion in the study, or before any data is collected, units should still allocate a study ID in REDCap. After screening for inclusion, the CRF will ask, “has the patient opted out?”, which will both allow monitoring of opt-out rates and act as a barrier to further data entry in the event of an affirmative response. When data has already been collected, any locally held information, except for the study ID and cross-referenced identifiers, should be deleted and/or destroyed in line with local policy. Changing the response to the

Date and Version No: 04/11/2024; Version 1.3

opt-out question will automatically prompt the deletion of any remaining data associated with that study-ID. As an additional safeguard, alongside checks for outlying data points, the central study team will regularly check the database for opt-outs and manually remove any remaining data held against the study-ID.

It will not be possible for patient data to be removed once the data collection period for each phase of the study has ended (i.e. six to eight weeks after the end of the recruitment period in each unit).

### **Qualitative study**

Consent to enter the study must be sought from each participant only after a full explanation has been given, a participant information sheet offered, and time allowed for consideration. Signed participant consent should be obtained and, to minimise hard-copy and to facilitate remote consent, eConsent will be obtained using the relevant REDCap modules\*. The right of the participant to refuse to participate without giving reasons must be respected. All participants are free to withdraw at any time from the interview, without giving reasons and without prejudicing their clinical treatment or professional situation.

## **4.4 STUDY ASSESSMENTS/ INTERVENTIONS**

### **Cross-sectional study:**

No deviation from routine patient care is required. The cross-sectional study will collect baseline information about the patient's background, including age, ethnicity, co-morbidity, BMI, pre-operative investigations and intra-operative findings, which will largely be available from the patient's written and digital records. The diagnosis/diagnoses of the postoperative histopathology report will be collected once available and is considered a result from the event of interest (the cholecystectomy).

Consequently, there is no longitudinal follow-up required.

### **Qualitative Study:**

The embedded qualitative study consists of carefully designed, semi-structured interviews which follow an interview guide, and can be found in the appendices. The analysis will occur contemporaneously, and the interview guide may be adjusted where appropriate, to maximise data richness, as the study progresses.

The fundamental questions to be answered are:

---

\* eConsent forms will exactly match the wording of approved paper consent forms.

Date and Version No: 04/11/2024; Version 1.3

- What are the participant's attitudes, experiences, and beliefs towards the risk of GBC?
- How supportive are participants of the concept of SHA in routine cholecystectomy?
- What perceived problems and barriers exist around introducing SHA in the UK?

Participants will undergo contact by the research team or by collaborators at the following time points.

All events may be either face-to-face, or remotely.

1. Identification

Participants will be contacted either by a member of the research team at University Hospitals Plymouth NHS Trust, or by a collaborator at a participating unit, as previously described. At this stage, they will be informed of the study and invited to make contact with the central research team to obtain more information.

2. Initial information, including provision of PIS

Participants will be contacted by an appropriate researcher from the central team, and provided with an explanation of the study, a copy of the PIS and an opportunity to ask any questions pertinent to their decision to participate. A minimum of 24 hours for the participant to consider their decision is required and the participant should indicate their agreement in principle before an interview is arranged.

3. Possible further liaison regarding logistics of interview arrangements

Further contact may be necessary, to make suitable arrangements for an interview to take place, or to answer any supplementary questions.

4. Interview

A qualitative researcher will meet with participants, either face to face or via MS Teams, as outlined elsewhere. At this contact, a final opportunity to ask questions will be offered, the consent form will be completed and the interview will be conducted.

5. Member checking (optional)

As outlined elsewhere, participants will be emailed transcripts and reports and invited to comment on them. This activity is strictly optional.

#### **4.5 DEFINITION OF END OF STUDY**

This is defined as the date of the last visit of the last participant undergoing the study. The Sponsor will notify the REC, in writing, within 90 days of the end of the study.

Date and Version No: 04/11/2024; Version 1.3

## 5. SAFETY REPORTING

Given the purely observational nature of this study, safety reporting is not applicable and there are no defined or undefined Serious Adverse Events.

## 6. STATISTICS

### 6.1 THE NUMBER OF PARTICIPANTS

#### **Cross-sectional study:**

The required power to develop a diagnostic score for iGBC, assuming a 0.2% prevalence, Nagelkerke's  $R^2$  of 0.3 and 20 diagnostic parameters, is 20,996. Allowing for a 20% rate of incomplete data, 26,245 participants would be required. It is possible that, following the feasibility study, it will be clear that more than 20 diagnostic parameters are required. The study will, therefore, aim to recruit up to 30,000 participants to ensure adequate power.

An internal pilot study will be undertaken between 8 participating units to ensure the feasibility of recruiting so many participants and calibrating the final recruitment target. Data collection will be paused at the first of 500 participants between all participating units or six months of completed data collection in each participating unit, allowing for the internal pilot to be evaluated. For a sample size of 500, an iGBC incidence of 0.2% will be estimated with a margin of error of +/- 0.39%. Rates of recruitment, completeness of data, and events will be evaluated. The assumptions above will be adjusted, and the corrected data will be used to re-calculate the final recruitment target before data collection for the complete cross-sectional study begins.

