## 1. INTRODUCTION

### 1.1 BACKGROUND

Incidental Gallbladder Cancer (iGBC) is a rare diagnosis following cholecystectomy, which is a common operation normally performed for symptomatic gallstone disease (1,2). Less common benign indications include gallbladder dyskinesia and gallbladder polyps. Overall, 67,819 cholecystectomies were performed in NHS England and Wales in the year to March 2022 and it is standard practice in the UK for cholecystectomy specimens to be sent for Routine Histological Analysis (RHA) to exclude underlying iGBC(1,3). The United Kingdom (UK) has a low incidence of iGBC of between 0.14-0.3%, which contrasts with high-incidence countries, for example in South America and South Asia, where it is as high as 1.18% (4–12). Other, non-cancerous abnormalities, termed Benign Histological Changes (BHC), such as Xanthogranulomatous Cholecystitis (XC) and Gallbladder Dysplasia (GBD), can be challenging to diagnose or differentiate from cancer macroscopically and therefore require histological examination. Combined, iGBC and BHC have an incidence in the UK of around 2% (4,6,13).

RHA is not unique to the UK, and is practised in most high-income countries, however it is expensive and requires examination of thousands of unremarkable gallbladders to diagnose relatively few patients with iGBC(1,8,10,14). We conservatively estimate that the cost of RHA in routine cholecystectomy is at least £5,055,228.26 annually, based on an historic estimate of the cost of processing individual specimens multiplied by the volume of cholecystectomies quoted above (1,8). In addition to the financial costs incurred by RHA, processing so many gallbladder specimens puts enormous pressure on histopathology services who are acknowledged to be overburdened and under resourced(15,16). This volume of specimens is particularly significant at present, as subsequent delays in processing NHS cancer specimens can anecdotally reach 4- 6 weeks, potentially delaying decisions on adjuvant treatment (e.g. chemotherapy) which, in some cases, may affect overall survival(17). As the incidence of iGBC is so low, it has been argued that sending every gallbladder specimen for RHA is unnecessary and could be replaced with Selective Histological Analysis (SHA), whereby gallbladders with no significant risk of iGBC or BHC would not be sent for histopathology(3,5,8–11,18–20).

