When comparing the populations in question, a further problem with the use of these scores arises. Compared to other European countries where patients are often operated within days of presentation, NHS patients wait longer for their cholecystectomies and therefore risk recurrent inflammation (35–43). In this post-COVID-19 era, a higher proportion of UK cholecystectomies are being performed for inflammatory indications, and this may suggest that the UK prevalence of iGBC will increase or the prognosis be poorer(7,23,35). As a consequence, we are unable to generalise the findings of the Swedish and Dutch studies to our own population and there is, therefore, a need for a high quality and comprehensive diagnostic modelling study of UK patients, to accurately identify and stratify the risk of iGBC.

This study aims to collect the data required to develop a high-fidelity, clinically applicable diagnostic score with a high negative predictive value, and has the potential to facilitate SHA and early identification of patients at high-risk of iGBC in this country.

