## 6.3 ANALYSIS OF ENDPOINTS

### Cross-sectional Study

#### a. Internal pilot analysis

Descriptive statistics (including means, standard deviations, medians, inter-quartile ranges and ranges, as appropriate for continuous variables and frequency and percentage for categorical variables) will be summarised for all demographics and potential predictive factors of iGBC collected.

The prevalence of iGBC and BHC will be presented as a percentage with confidence intervals.

The number of patients undergoing cholecystectomy, the number of patients eligible, the number of patients (and percentage) recruited, and the number of patients (and percentage) undergoing the procedure will be summarised overall and by site.

The level of data completeness (demographics, potential risk factors and outcomes) will be summarised by frequency and percentages overall and by site.

Descriptive statistics will be used for

- rates of iGBC and BHC in the pilot population
- rates of recruitment of patients to the study
- data completeness

The dataset will be evaluated to identify commonly incomplete data points (core data points for which completeness is <80%). Units and collaborators will then be surveyed to evaluate the challenges associated with these areas. Following the result of this survey, the study team will discuss each incomplete data point and make suitable adjustments to the power calculation and data points for collection according to the figure below.

Date and Version No: 04/11/2024; Version 1.3

	Variable with large effect size or significance for iGBC in pilot, or in previous studies	Variable with low or uncertain effect size or significance for iGBC
Completeness likely to improve to >80% following intervention (e.g. change in the phrasing of a question or definition, change to patient record sheet)	Retain data point for full study	Retain data point for full study
Completeness unlikely to improve following intervention	Retain data point for full study, consider adjusting power calculations to accommodate level of completeness achieved in pilot	Consider whether omitting data point from full study is justified

Rates of recruitment will be considered in the context of the power calculation and the time initially allocated to complete data collection. Where necessary, proposed timeframes will be adjusted in the context of the power calculation and with details of potential participating units, prior to data collection for the full study beginning.

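### The pilot's ±0.39% margin for a 0.2% incidence is a normal approximation at one expected cancer, and nothing stops so small a count from re-setting the prevalence behind the recruitment target

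*Protocol*

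**What the plan says.** Section 6.1 (Cross-sectional study) bases the full-study size on a 0.2% prevalence, a Nagelkerke R² of 0.3 and 20 diagnostic parameters. This gives 20,996, or 26,245 after a 20% allowance for incomplete data.

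The internal pilot stops at 500 participants or after six months in each unit, whichever comes first; the Study Summary gives its size as 300–500. One of its stated purposes is "calibrating the final recruitment target". Its precision is given as: "For a sample size of 500, an iGBC incidence of 0.2% will be estimated with a margin of error of +/- 0.39" per cent.

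The next sentences read: "Rates of recruitment, completeness of data, and events will be evaluated", and then "The assumptions above will be adjusted, and the corrected data will be used to re-calculate the final recruitment target".

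Section 6.3 (Internal pilot analysis) describes two narrower routes. For incompletely recorded data points the team will "make suitable adjustments to the power calculation and data points for collection according to the figure below". For recruitment rates, "Where necessary, proposed timeframes will be adjusted in the context of the power calculation". Neither route mentions prevalence, either to include it or to exempt it.

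On the prevalence itself, section 1.1 says "The United Kingdom (UK) has a low incidence of iGBC of between 0.14-0.3" per cent. It adds, of the higher proportion of cholecystectomies now done for inflammatory indications, that "this may suggest that the UK prevalence of iGBC will increase".

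**The concern.** A symmetric margin of 0.39 points around 0.2% reaches below zero, which a proportion cannot do. It comes from a normal approximation applied where about one event is expected. A reader would take the pilot to bound the incidence at roughly 0.6%, when the exact upper limit after one case is nearly twice that.

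This matters beyond presentation because of what follows in the same section. The assumptions to be adjusted include the 0.2% prevalence, and events are among the quantities evaluated. Read literally, a count of zero, one or two cancers may change the prevalence and hence the recruitment target. For a rare-event prediction model the target depends strongly on prevalence, so chance in the pilot could leave the main study too small. The protocol does not say that the raw pilot proportion will replace 0.2%; the difficulty is that its wording permits this.

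**Working it through.** **Inputs.** n = 500, p = 0.2% and the ±0.39% margin come from section 6.1. The smaller pilot size of 300 comes from the Study Summary, and the UK range of 0.14–0.3% from section 1.1. The confidence level is not stated; 95% is assumed because it reproduces the figure.

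**1. Reproducing the stated margin.** Wald half-width = z × √(p(1 − p)/n).
- 95%: 1.96 × √(0.002 × 0.998/500) = 0.3916%, which matches 0.39%.
- 90% gives 0.33% and 99% gives 0.51%, so neither matches.
- Implied interval: 0.2% ± 0.39% = −0.19% to 0.59%.

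**2. Why the approximation fails.** Expected cases = 500 × 0.002 = 1.0. If the true rate is 0.2%, the nominal 95% Wald interval computed from the observed count covers it about 63% of the time. With no case, that interval collapses to zero width.

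**3. Exact (Clopper–Pearson) 95% intervals.**

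| Cases | n = 500 | n = 300 |
|---|---|---|
| 0 | 0 to 0.74% | 0 to 1.22% |
| 1 | 0.005% to 1.11% | 0.008% to 1.84% |
| 2 | 0.05% to 1.44% | – |
| 3 | 0.12% to 1.74% | – |

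For one case in 500 the upper arm is 1.109 − 0.200 = 0.909 points, against the stated 0.39.

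**4. Can the pilot distinguish prevalences within the cited UK range?** All four intervals at n = 500 contain 0.14–0.3% in full. The binomial chances with n = 500 are:

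| True rate | No case | 0 to 3 cases |
|---|---|---|
| 0.14% | 50% | 99% |
| 0.2% | 37% | 98% |
| 0.3% | 22% | 93% |

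At n = 300 and a true 0.2%, 0.6 cases are expected and the chance of none is 55%.

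**5. Sensitivity of the target to prevalence (illustration only).** The shrinkage criterion is n = P / [(S − 1) ln(1 − R²cs/S)], with P = 20 and R²cs = 0.3 × its maximum at the given prevalence. S = 0.90 is assumed because the protocol does not state it. At 0.2% the maximum is 0.02844, so R²cs = 0.00853 and n = 20,996; dividing by 0.8 gives 26,245. Both protocol figures reproduce. Changing only the prevalence:

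| Prevalence | Before allowance | After ÷ 0.8 |
|---|---|---|
| 0.14% | 28,506 | 35,633 |
| 0.2% | 20,996 | 26,245 |
| 0.3% | 14,892 | 18,615 |
| 0.4% (2 cases in 500) | 11,707 | 14,634 |

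If the raw proportion were used, two cases would cut the target by (26,245 − 14,634)/26,245 = 44%. If the true rate were still 0.2%, 11,707 complete records would yield 11,707 × 0.002 ≈ 23 cancers, against 20,996 × 0.002 ≈ 42 as planned. Two or more cases have a 26% chance at a true 0.2%. With no case the formula has no solution.

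**The case against.** Five points can be made for the plan.

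- **The figure is not miscalculated.** This is correct. The fault lies in the choice of method.
- **As a planning statement it is roughly right.** At a true 0.2%, the estimate falls within 0.39 points of the truth when there are 0 to 2 cases, a 92% chance. The exact lower arm for one case is about 0.195 points, shorter than stated, and the exact interval for no case (0.735 points wide) is narrower than the Wald width of 0.78. These figures hold, but they do not rescue a symmetric margin that includes negative rates and understates the upper uncertainty.
- **The pilot's interval method is not fixed as Wald and may be left to the SAP.** That is fair for reporting. The ±0.39% itself is printed in the protocol as the pilot's precision.
- **Section 6.3 links the power calculation only to completeness, and no progression criterion uses the event count.** This is a real limit: substituting the raw proportion is not a stated procedure, and the fall to 14,634 is only an illustration. But section 6.1 has events evaluated and the assumptions adjusted, without excluding prevalence.
- **A high count would be informative.** Four cases give 0.22% to 2.04%, which excludes 0.2%; five give 0.33% to 2.32%, which excludes the whole UK range. Four or more have a 2% chance at a true 0.2%. Keeping 0.2% in that event leaves the target larger, and external evidence could still change it.

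The objection that the re-calculation should also name R² carries little weight, since about one event could not inform R² either.

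**Conclusion.** The concern holds. The ±0.39% is a correctly computed 95% Wald half-width that is not valid at one expected case. For one case in 500 the exact interval is 0.005% to 1.11%, so the upper uncertainty is 0.91 points rather than 0.39, and precision is worse if the pilot closes nearer 300. The most likely pilot results, 0 to 3 cases, cannot separate prevalences within the UK range already cited, yet the re-calculation wording leaves prevalence open to adjustment from them.

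The interval results rest on the binomial model and the inferred 95% level. The effect on the target also rests on an assumed shrinkage of 0.90 and on a substitution that the protocol permits but does not state. The point does not invalidate the study. It should be corrected before the pilot count is used to re-calculate the target.

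**What to change.** Make two wording changes in section 6.1.

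1. Replace the ±0.39% sentence with: *With 500 participants and a true incidence of 0.2%, one case is expected and the chance of no case is 37%; the exact 95% interval would be 0 to 0.74% for 0/500 and 0.005% to 1.11% for 1/500.* Report the pilot rate with its exact interval.

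2. Amend the re-calculation sentence to: *The final target will be re-calculated from the data completeness achieved in the pilot and the number of diagnostic parameters. The prevalence assumption will not be re-set from the pilot event count alone; it will stay at 0.2%, with 0.14% and 0.3% as sensitivity cases, unless external evidence supports a change. Recruitment rate will be used to adjust timeframes and centres (section 6.3).*

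This keeps prevalence open to the rise that section 1.1 anticipates. On the illustrative formula the 0.14% case needs 35,633, above the 30,000 ceiling, so the team should say how it would respond to that case.

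The cost is protocol wording only, with no added patients or data. The stated pilot precision becomes less favourable, and the pilot no longer recalibrates prevalence by itself.
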